**6.1.3**

- Pre-surgery lesion size on CEDM, on 90 to 120 second, 5 minute and 10 minute time points will be assessed using three maximal dimensions.
- On pre-surgery CEDM, association of any residual calcifications with enhancement will be recorded
- The largest single focus of enhancement will be recorded, as well as an overall residual tumor volume (single maximal dimension)
- The association of post biopsy clip with the enhancement will be recorded.

## **6.2 Safety/tolerability**

Analyses will be performed for all patients having undergone at least one baseline and one mid or post therapy CEDM. We will perform standard of care pre and post CEDM monitoring in the immediate post CEDM phase, record and grade any reactions.

We will also ask patients to fill out a survey regarding their comfort level with **CEDM (APPENDIX B)** before their surgery.

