##### 3.2.6

Eligible patients will be imaged at baseline (before initiation of neoadjuvant chemotherapy or endocrine therapy), early (2-4 cycles of neoadjuvant therapy) and late (after completion of neoadjuvant chemotherapy or endocrine therapy) timepoints with mammography. CEDM will be done within 2 weeks of the specified timepoint. Three dimensional orthogonal measurements will be obtained in all timepoints. Additional sites of disease in the ipsilateral or contralateral breast identified by CEDM will be recorded and reported. ACR BI-RADS MRI lexicon will be used for reporting.

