##### 4.1.1

The risks of CEDM include the risks of contrast administration including allergic reactions and renal function abnormalities. Just as with CT, patients will be screened for allergy history and possible renal function abnormalities. Allergic or physiologic reaction are reported to occur in less than 1% of patients when using low osmolar contrast agents although this increases in patients with prior reactions (11,12). Severe acute reactions occur in 4/10,000 (0.04%) of patients (13). Any contrast reaction will be handled in accordance with the Radiology Department's Contrast-Reaction Guidelines  
[https://hs.swmed.edu/communities\\_collaboration/radpoint/clinicaloperations/Practice%20Guidelines%20%20Procedures/Contrast%20Reactions%20-](https://hs.swmed.edu/communities_collaboration/radpoint/clinicaloperations/Practice%20Guidelines%20%20Procedures/Contrast%20Reactions%20-)

%20Pocket%20Guide.pdf#search=contrast%20reaction)Concomitant Medications/Treatments

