#### **4.5 Subject Replacement**

Loss of any subjects before second timepoint CEDM occurs will result in subject replacement.

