**5.5 Removal of Subjects from Study**

Subjects can be taken off the study at any time at their own request, or they may be withdrawn at the discretion of the investigator for safety, behavioral or administrative reasons. The reason(s) for discontinuation will be documented and may include:

- 5.5.1 Subject voluntarily withdraws from treatment (follow-up permitted);
- 5.5.2 Subject withdraws consent (termination of treatment and follow-up);
- 5.5.6 Treating physician judges continuation on the study would not be in the subject's best interest;
- 5.5.7 Subject becomes pregnant (pregnancy to be reported along same timelines as a serious adverse event);
- 5.5.9 Patient develops moderate to severe reaction to contrast (as defined by the Department's guidelines for iodinated contrast) over the course of neoadjuvant therapy follow-up. Mild reactions will be considered for pre-medication and decided on a case by case basis.

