### **8.3 Data Analyses**

Descriptive statistics will be produced for all patients; frequencies and percentages for categorical measures and means, medians, standard deviations, and ranges for continuous measures. The number of cancer foci identified by each imaging modality will be compared. Tumors will be categorized according to immunohistochemical approximated molecular profiles (Luminal A, Luminal B, Triple-negative and HER-2 amplified). Additional exploratory analyses will be performed as needed.

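### The only analysis-set rule under Safety/tolerability requires a second CEDM, so a patient who leaves after a contrast reaction at baseline is not counted

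*Combined protocol and SAP*

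**What the plan says.** Section 6.2 is headed Safety/tolerability. Its opening sentence is "Analyses will be performed for all patients having undergone at least one baseline and one mid or post therapy CEDM". The next sentence provides for monitoring around each exam and for recording and grading reactions, and the section ends with the pre-operative comfort survey. No other population is given there.

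Section 8.3 says "Descriptive statistics will be produced for all patients; frequencies and percentages for categorical measures". It does not define all patients, mention contrast reactions or refer to 6.2.

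Three other places decide who reaches a second CEDM:

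- Section 4.0 (the paragraph numbered 3.2.6) puts the first CEDM before any neoadjuvant therapy.
- Section 5.5 lets patients leave at their own request, and says "they may be withdrawn at the discretion of the investigator for safety, behavioral or administrative reasons". Item 5.5.9 lists a moderate to severe contrast reaction as a reason, but ties it to reactions "over the course of neoadjuvant therapy follow-up". It adds: "Mild reactions will be considered for pre-medication and decided on a case by case basis".
- Section 4.5 says "Loss of any subjects before second timepoint CEDM occurs will result in subject replacement".

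On risk, section 4.1.1 says "Allergic or physiologic reaction are reported to occur in less than 1% of patients when using low osmolar contrast agents", and puts severe acute reactions at 4 in 10,000 (0.04%).

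**The concern.** Contrast reaction is one of the CEDM risks that section 4.1.1 names, and the baseline exam is the first study exposure to contrast. A safety denominator that requires a later CEDM leaves out the patients most likely to have stopped because of the first one. Membership of the set then depends partly on the outcome it would describe. Replacement under 4.5 fills the vacant place with a patient who got as far as a second exam, so the reported set still numbers 100 and the omission does not show.

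At stake is how the study describes CEDM tolerability, for example when the larger multi-institutional study foreseen in section 8.2 is designed. The primary accuracy analysis and the precision figures in 8.2 are not affected.

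**Working it through.** **Textual check.** Take a patient who reacts at the baseline exam and leaves.

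1. Exams done: one. The 6.2 rule needs a baseline exam and a later one, so the patient is outside the set.
2. Route out: the patient's own request or discretionary safety withdrawal (5.5). Item 5.5.9 may also apply, but its wording refers to therapy follow-up and the baseline exam precedes therapy, so its reach is unclear. The point does not depend on 5.5.9.
3. Replacement: the loss is before the second CEDM, so 4.5 applies.
4. Other text: 8.3 refers to all patients in general terms. No section defines a contrast-exposed set.

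**Size.** The plan gives no figure for a reaction analysis, so there is none to reproduce. From the plan: 100 patients (8.2), three exams (5.4), severe rate 4/10,000 = 0.0004, any reaction below 1% (4.1.1). Assumptions:

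- *p* = 0.01, the any-reaction risk per exam. This takes the upper bound, reads a per-patient rate as per-exam, and holds it equal at three exams.
- *q* is the fraction of baseline exams that end in reaction-related withdrawal. The documents do not give it. The range shown is 0.0004 (only severe reactors leave) to 0.01 (every reactor leaves).
- *u* is loss after baseline for unrelated reasons, independent of reactions. It is not given either; 0 to 20% is shown.

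Formulas:

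- Expected omitted per 100 = 100*q*; chance of at least one = 1 − (1 − *q*)^100.
- Baseline-exam rate in the 6.2 set = (*p* − *q*)/(1 − *q*), against *p* = 1.00% in all exposed.
- Per-patient rate in the 6.2 set = 1 − (1 − *p*)³/(1 − *q*), which does not depend on *u*.
- Per-patient rate in all exposed = *p* + (1 − *p*)(1 − *u*)[1 − (1 − *p*)²] = 0.01 + 0.019701(1 − *u*).

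| *q* | Omitted per 100 | Chance of ≥1 | Baseline-exam rate, 6.2 set | Per-patient rate, 6.2 set |
|---|---|---|---|---|
| 0.0004 | 0.04 | 3.9% | 0.96% | 2.93% |
| 0.0025 | 0.25 | 22.1% | 0.75% | 2.73% |
| 0.005 | 0.5 | 39.4% | 0.50% | 2.48% |
| 0.01 | 1 | 63.4% | 0% | 1.99% |

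Per-patient rate in all exposed, and relative difference of the 6.2 rate from it:

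| *u* | All exposed | *q* = 0.0004 | *q* = 0.0025 | *q* = 0.005 | *q* = 0.01 |
|---|---|---|---|---|---|
| 0 | 2.97% | −1.3% | −8.2% | −16.4% | −33.0% |
| 5% | 2.87% | +2.1% | −5.0% | −13.5% | −30.7% |
| 10% | 2.77% | +5.7% | −1.7% | −10.5% | −28.2% |
| 20% | 2.58% | +13.8% | +5.9% | −3.6% | −22.8% |

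The 6.2 per-patient rate is below the all-exposed rate only if *q* exceeds about 0.10%, 0.20% or 0.40% at *u* = 5%, 10% or 20%. The reason is that patients lost for unrelated reasons after one exam had less exposure, and dropping them raises the rate. The baseline-exam rate falls whenever a reactor leaves, whatever *u* is.

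**One omitted case.** Suppose the only reactor is one such patient, who is replaced, with no other loss. The 6.2 set gives 0/100 (exact 95% CI 0 to 3.6%). All exposed gives 1/101 = 1.0% (0.03 to 5.4%).

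**The case against.** The strongest reply is that the 6.2 sentence is not a safety rule. It says only that analyses will be done, without saying which. A baseline plus a later exam is what a change-from-baseline response measure needs, and it matches the replacement rule in 4.5. The sentence on recording reactions carries no restriction. This reading is plausible. If it is right, the sentence is under the wrong heading and the safety summary has no stated population, so the section still needs the same correction.

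Second, 8.3 is a general sentence that does not name reactions, so it is not a rival safety definition. That is correct: the two passages are unreconciled, not in outright contradiction. If 8.3 was meant to govern graded reactions, the plan should say so.

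Third, no event is lost to oversight. Section 7.1 records the type and severity of reactions, 7.2 sends serious events to the monitoring committee and summarises others to the IRB, and 9.4 has adverse events reviewed quarterly. This stands, but these are collection and reporting channels and do not set the denominator of a study rate.

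Fourth, the size is tiny. No objective or endpoint is a reaction rate. Section 3.2 excludes patients with prior contrast anaphylaxis or iodinated-contrast allergy, which would tend to lower the risk. Reading the cited rate per exam gives about 3% per patient, above the cited bound of 1% of patients. If that 1% were instead spread over three exams, the per-exam risk would be 1 − 0.99^(1/3) = 0.33%, and the ceiling would fall from 1 to 0.33 omitted patients per 100. All of this stands and limits the point to a minor one.

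**Conclusion.** The concern holds, as a minor point. As written, the only analysis set under the safety heading leaves out a patient who leaves after a contrast reaction at baseline, and nothing in the plan reconciles this with all patients in 8.3.

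The expected omission is 0.04 patients per 100 baseline exams at the cited severe rate. The ceiling is 1 per 100, which is unlikely because 5.5.9 handles mild reactions case by case. The baseline-exam reaction rate is biased downwards. The direction for the per-patient rate depends on unrelated dropout, which the documents do not give. The rates rest on the assumed 1% per-exam risk, equal risk at each exam, and the withdrawal and loss ranges shown. The textual finding rests on none of these. Confidence is medium, because the sentence may have been meant for the response analyses.

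**What to change.** In 6.2, state that contrast reactions are summarised for every patient who received at least one CEDM contrast injection, including withdrawn and replaced patients. State separately that the baseline-plus-later-CEDM rule applies to the response analyses. Add a cross-reference so that 6.2 and 8.3 use the same definition of all patients. Reporting reactions per patient and per exam by timepoint, with exact confidence intervals, would be useful but is optional. The reach of 5.5.9 to the baseline exam should also be made clear; which way is for the investigators to decide.

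The cost is one or two sentences and a cross-reference. Reactions are already recorded under 7.1, so no new data are needed, and sample size and the primary endpoint do not change. The reported rate may be less favourable. The change does not recover survey responses from patients who leave early, because the survey is given before surgery.

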**5.1.2** **Medical history, and reviewing subject eligibility criteria previous and concomitant medications**

#### **Informed Consent**

#### **5.2 Procedures During CEDM**

CEDM will be performed using UTSW Imaging Protocol (**attached, Appendix A**), including monitoring for immediate contrast reactions.

Discussion of additional findings: All breast imaging findings are routinely discussed with the patient by the radiologist immediately after imaging in our clinical practice. Additional findings identified on CEDM will be addressed similar to additional disease noted on ultrasound or breast MRI per standard of care.

Study Number – Insert PRMC Assigned SCCC- Protocol Number (found on the PRMC approval letter)

---

Survey of patient experience with CEDM and other pre-operative imaging such as MRI will be collected after CEDM is performed, optimally at pre-operative time point (Appendix B).

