**5.4 Time and Events Table**

	Baseline	Mid chemotherapy	Pre-Operative
Informed Consent	x		
History and allergies	X	X	X
CEDM	X	X	X
QUESTIONNAIRE			X

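### The only scheduled patient survey is pre-operative, so early stoppers may go unsurveyed and the exploratory CEDM comfort, scan-time and satisfaction scores risk upward completer selection

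*Combined protocol and SAP*

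**What the plan says.** Three places set the timing of the survey, and they differ in strictness.

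- Section 5.2: the survey "will be collected after CEDM is performed, optimally at pre-operative time point". This states a preferred time, not the only permitted one.
- Section 5.4, Time and Events table: the row "QUESTIONNAIRE" has one mark, under Pre-Operative.
- Section 6.2: "We will also ask patients to fill out a survey regarding their comfort level with" CEDM before their surgery. No visit is named.

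The rules on who remains to be surveyed are in other sections.

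- Section 5.5 lists reasons for leaving the study, among them "Patient develops moderate to severe reaction to contrast" (5.5.9), voluntary withdrawal with follow-up still allowed (5.5.1: "Subject voluntarily withdraws from treatment (follow-up permitted"), and withdrawal of consent, which ends follow-up (5.5.2).
- Section 4.4 expects removed subjects to be followed per protocol.
- Section 4.5: "Loss of any subjects before second timepoint CEDM occurs will result in subject replacement".
- Section 6.2, Safety/tolerability: "Analyses will be performed for all patients having undergone at least one baseline and one mid or post therapy CEDM".

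Survey scores for patient experience are an exploratory endpoint (2.4.3), and preference between CEDM and MRI is an exploratory objective (2.3.2). In Appendix B, items B, D and F rate CEDM, items A, C and E rate MRI and are left blank if no MRI was done, and items G and H (preference) are only for patients who also had MRI.

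**The concern.** A tolerability rating collected once, at the end of a three-scan schedule, is collected after most of the opportunities to stop because of intolerance have passed. A patient who reacts to contrast at the first or second CEDM, or who finds the scan unpleasant and declines the next one, has no scheduled occasion to say so on the form. The analysis-set rule in 6.2 selects in the same direction: a patient who stops after the baseline scan is outside the set even if someone does obtain a survey.

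At stake is what the scores on items B, D and F describe. The aim is experience among patients given CEDM; the schedule tends to deliver experience among patients who kept having it. Because no earlier score is scheduled, the data could not show whether the two differ. Section 8.2 says the results are meant to help design a multi-institutional study, where acceptability of the test would be useful information.

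**Working it through.** **Plan's own figures.** Section 8.2 gives precision for sensitivity (±0.17), specificity (±0.14), AUC (±0.12) and the Spearman correlation (width 0.39). These reproduce (0.167, 0.135, 0.113 to 0.116, 0.393), but the point does not rest on them. The plan states no figure for the survey.

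**Step 1. Can an early stopper be surveyed?** Yes under 5.2 and 6.2, which permit any time after CEDM and before surgery, and under 4.4 and 5.5.1, which expect or permit follow-up. Nothing requires it: 5.4 schedules only the pre-operative visit, and no section sets a survey at discontinuation. After withdrawal of consent (5.5.2) it is no longer possible.

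**Step 2. How many would be missed through contrast reactions?** Section 4.1.1 gives under 1% for any allergic or physiologic reaction and 0.04% for severe acute reactions. I treat these as rates per examination, independent between examinations. Only the first two CEDMs count, because a patient who reacts at the third is already at the pre-operative visit.

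Expected patients per 100 = 100 × (1 − (1 − r)²)

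- r = 0.01: 100 × (1 − 0.99²) = 1.99, so under 2 per 100
- r = 0.0004: 100 × (1 − 0.9996²) = 0.08 per 100

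The first is an upper bound for removals under 5.5.9, which need a moderate to severe reaction.

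**Step 3. Shift in the mean score.** If a fraction f is unsurveyed, the surveyed mean exceeds the mean in all patients by

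shift = f × (mean of surveyed − mean of unsurveyed)

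The documents give no score means. Assume 4 on the 1-5 scale among those surveyed and 1 to 3 among those not surveyed, a gap of 3 to 1 points.

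| Unsurveyed | 1-point gap | 2-point gap | 3-point gap |
|---|---|---|---|
| 2% (reactions, upper bound) | 0.02 | 0.04 | 0.06 |
| 5% (assumed) | 0.05 | 0.10 | 0.15 |
| 10% (assumed) | 0.10 | 0.20 | 0.30 |
| 15% (assumed) | 0.15 | 0.30 | 0.45 |

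**Step 4. Against sampling error.** With an assumed SD of 1.0 and n = 100, the 95% half-width is 1.96 × 1.0 / √100 = 0.196. The shift equals this when f = 0.196 / gap:

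- 3-point gap: 6.5% unsurveyed
- 2-point gap: 9.8%
- 1-point gap: 19.6%

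Reactions alone cannot reach those shares. Withdrawals for discomfort would have to supply most of them, and the documents give no rate for such withdrawals.

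**Step 5. Does replacement matter?** Replacing early losses (4.5) adds completers. It does not change the expected score among completers and does not enter the formula. Its only effect is to keep the count of completed surveys up.

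**The case against.** The strongest case on the other side has five parts.

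1. *The schedule is looser than the table suggests.* A reader might infer from 5.4 that early stoppers are never asked. The documents do not support that: 5.2 states a preference, 6.2 says only before surgery, and 4.4 and 5.5.1 leave follow-up open. This stands. What remains is that an earlier survey is allowed but not scheduled.
2. *The documented reaction rate is tiny, and patients at higher risk are excluded* (3.2.4, 3.2.5). This stands, and it limits the reaction component to the first row of the table. It does not address discomfort.
3. *Not every stopper is a dissatisfied one.* Section 5.5 also lists pregnancy, physician judgement and administrative reasons. This stands, so the larger rows of the table are illustrations and not estimates.
4. *Intolerance is recorded elsewhere.* Reactions are recorded and graded (6.2, 7.1), and reasons for discontinuation are documented (5.5). This stands for safety. It does not supply comfort, scan-time or satisfaction ratings for those patients.
5. *One late survey is a reasonable design,* because the patient then rates CEDM and MRI side by side after the full imaging experience. This stands, and it is a reason to keep the pre-operative survey and add to it.

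**Conclusion.** The point holds as a risk of upward completer selection in items B, D and F. It rests on the single scheduled survey in 5.4, the absence of any survey at discontinuation, and the 6.2 requirement for a baseline and a later CEDM.

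From contrast reactions the size is at most about 0.06 points on a 5-point item, given the under-1% rate and an assumed 3-point gap. Beyond that it depends on discomfort withdrawals: 0.05 to 0.30 points if 5-15% are unsurveyed with a 1-2 point gap. Both of those inputs are assumptions.

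A reader might go further and infer that the scores are biased in favour of CEDM, including the preference over MRI. The documents do not support this. They give no rate of stopping for discomfort, so bias is possible but not shown. For preference, items G and H are answered only by patients who had MRI, and MRI is not required (4.2). Patients who could not tolerate MRI are therefore also missing, which pushes the other way, and the net direction is not settled.

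The consequence is confined to an exploratory endpoint with no hypothesis or decision rule attached. The primary AUC endpoint and the safety record are unaffected. This is an inexpensive improvement and not a flaw in the main design.

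**What to change.** - Reconcile 5.2, 5.4 and 6.2 so that all three state the same survey times.
- Collect items B, D and F on the day of the baseline CEDM, ideally at each CEDM, and at discontinuation where the patient agrees. The baseline form matters most, because it also captures patients who later withdraw consent.
- Keep the full Appendix B survey pre-operatively, so that the MRI comparison and the preference items are still answered side by side.
- Summarise B, D and F by timepoint for all patients with at least one CEDM. Do not pool each patient's last score, since a rating after one scan and a rating after three measure different experience.
- Compare the baseline scores of patients who did and did not reach the pre-operative survey. This shows directly whether selection occurred.
- Report the number not surveyed, with reasons.

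Cost: one or two extra completions of a three-item form per patient, with no added visit, procedure or staff, and a minor amendment that needs IRB approval before use (9.6). The downside is a slight extra burden on patients.

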## **6.3 Pathology**

Final histopathology for correlation will include the size of residual tumor (ypT), tumor cellularity (%) and amount of DCIS (%). Per AJCC8th edition [Amin MB, Edge SB, Greene FL, et al, eds. AJCC Cancer Staging Manual. 8th ed. New York: Springer; 2017] (ypT) is based on the largest continuous focus of residual invasive cancer, if present. Treatment-related fibrosis adjacent to residual invasive carcinoma or between foci of residual cancer is not included in the ypT maximum dimension. When multiple foci of residual tumor are present, the (m) modifier is included.

In addition, we will record ki67 index pre and post therapy and its potential correlation with the degree of tumor response seen on CEDM.

The agreement between pre-operative CEDM measurements and mammography in categorizing tumor response RCB0-I/ RCBII/RCBIII will be assessed using weighed kappa.

